6.4.7 Assessment of compliance with study medication

Participants will be asked to return used AIT (Grazax®) and AIT placebo blister packs and unused tablets at each study visit. Those participants with less than 75% compliance with study medication will be counselled. Use of rescue medications (section 6.4.8.1) will be assessed by medication score (Appendix 5). The participant will fill out a daily Medication Diary in which he/she will record the Tablet intake (Appendix 9).

6.4.8 Concomitant medication

6.4.8.1 Permitted Medications

The following rescue medications will be provided. These medications are considered standard of care and will be provided approximately 2 weeks before the start of the pollen season (May 2014) and throughout the pollen season:

- Antihistamine (e.g. desloratidine).
- Nasal corticosteroid (e.g. fluticasone propionate aqueous nasal spray).
- Ophthalmic antihistamine (e.g. olopatadine eye drops).

Use of the following rescue medications will be provided by the study only after participants are evaluated by the investigator. Evaluations may occur by phone contact or clinic visit.

- Oral corticosteroid (e.g. prednisolone).
- Short-acting beta-agonists (e.g. salbuterol).
- Inhaled corticosteroids (e.g. fluticasone).
- Combination long-acting beta-agonists or steroids (e.g. salmeterol/fluticasone).

Refer to **Appendix 7** for required medication washout periods prior to screening, nasal challenges and biopsies (V-1, V0b, V5, and V7).

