5.3 Clinical hypotheses

Grass pollen AIT treatment compared to placebo results in:

1. Suppression of the EPR to grass pollen nasal provocation.
2. Suppression of the EPR and LPR following intradermal grass pollen injection.
3. Reduction in seasonal symptoms and medication use.

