6.5.14 Visits

Atopic Participants:

Scheduled Visits (screening, randomisation and blinded treatment phase):

Where possible, all study visits should occur within the time limits specified below:

Screening Visit – Visit -1, from December 2013 to April 2014.

Visit – 0a, after screening and before Visit 0b.

Visit – 0b, from January 2014 to April 2014.

Visit – 1, after Visit – 0b.

Visit – 2, from February to May 2014.

Visit – 3, from March to May 2014.

Visit – 4, from April to June 2014.

Visit – 5, from May to August 2014.

Visit – 6, from July to October, 2014

Visit – 7, from January to April 2015.

Unblinded treatment phase

Visit- 8, January-March 2016

Visit- 9, January-March 2017

Unscheduled visits:

Unscheduled visits may be performed in the event that participants experience a disease exacerbation requiring treatment or because the participant prematurely terminates from the study (see section 6.3.3).

Visit -1:**Screening visit:**

Volunteers will attend the allergy unit at the Royal Brompton Hospital for approximately 2 hours. During this visit the following will be undertaken:

- Written informed consent before any study procedures are performed.
- Demographic data (sex, date of birth, ethnic origin, medical history).
- Allergic history - record of allergic symptoms and allergic medication taken by the subject during at least the last two years.
- Physical examination and observations (weight, height, blood pressure, heart rate, peak expiratory flow rate, peak nasal inspiratory flow and spirometry).
- Participants will mark a retrospective Global evaluation (GE) visual analogue scale (VAS) (scale 0-100 mm; **Appendix 1**) and complete a retrospective GE chart (**Appendix 2**) documenting the overall severity of their hay fever symptoms during the previous pollen season.
- Participants will complete a Mini Juniper Rhinitis Quality of Life Questionnaire (mRQLQ) (**Appendix 3**) and Global evaluation scores (**Appendix 4 and 5**) corresponding to current rhinitis symptoms and medications.
- Skin prick test - standard allergen test panel as described previously.
- Blood sampling of up to 20 ml for total IgE, specific IgE to Timothy grass pollen and total blood count will be taken.
- Nasal challenge with 5,000 BU/ml Timothy grass pollen extract with TNSS recorded after 5 minutes (**Appendix 6**).
- Recording of concomitant medication.
- Evaluation of inclusion and exclusion criteria.

Visit 0a:

1st Baseline Visit:

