Around 5 months after begin of AIT/placebo and during the pollen season participants will come to the hospital for 1.5 hours. During this visit the following will be undertaken (see also **Table 4**):

- A period of 15 minutes acclimatization to hospital environment and relative inactivity.
- Participants will mark questionnaires (**Appendix 3-5**) corresponding to symptoms and rescue medication use during the current pollen season.
- Furthermore the volunteers will undergo the same procedures as in Visit 0b, plus questionnaires and with the exception of the intradermal skin test and nasal challenge.

Table 4: Time line procedures at Visit 5

Time (hr:min)		Procedure
00:00	Arrival	
00:05	Blood	Blood sample (200ml)
00:15	Pre-lavage	GE VAS; mRQLQ; SMS, secretion collection
00:20	Pre-lavage	Nasal brushing
00:25	Nasal-lavage	
00:55	Post-lavage	Secretion collection

		Nasal biopsy
--	--	--------------

GE VAS; Global Evaluation visual analogue scale

mRQLQ; mini Rhinitis Quality of Life Questionnaires

SMS; symptom medication score

Visit 6:

After 6 months of treatment and shortly after the pollen season patients will mark a retrospective GE VAS (scale 0-100 mm; **Appendix 1**), the mRQLQ (**Appendix 3**) and complete a retrospective GE chart (**Appendix 2**) documenting the overall severity of their hay fever symptoms during the previous pollen season. Also a nasal allergen challenge with 5.000 BU/ml Timothy grass pollen allergen will be undertaken. We will record the Peak Flow as well as the response to challenge for one hour at 5, 15, 30 and 60 min with TNSS + VAS and PNIF.

Time (hr:min)		Procedure
-00:15	Arrival	TNSS+VAS; GE VAS, mRQLQ, GE, PNIF; Peak Flow
00:00	Nasal Challenge	5,000 BU/ml Timothy grass pollen allergen
00:05	Early Nasal response	TNSS + VAS; PNIF
00:15	Early Nasal response	TNSS + VAS; PNIF
00:30	Early Nasal response	TNSS + VAS; PNIF
01:00	Early Nasal response	TNSS + VAS; PNIF; PeakFlow

Visit 7:

After 12 months on treatment volunteers will attend the allergy unit for a period of 2 hours in the morning and 1 hour during the evening (3 hours). During this visit the same procedures as described at Visit 0b plus a blood sample of 200 ml will be undertaken (see also **Table 2**).

Non-atopic Participants:

Scheduled Visits (screening (Visit -1), one time point assessment (Visit 1):

Screening Visit – September 1st to November 30th, 2014.

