Appendix 5: Symptom and Medication Score

Please complete weekly on Wednesday during the pollen season from beginning of May until the end of July.

Symptom Score:

“How do you assess the severity of your hay fever symptoms when they were at their most severe during the last week (tick each single symptom)?”

Rhinoconjunctivitis / Hayfever Symptom		Symptoms			
		0 (None)	1 (Mild)	2 (Moderate)	3 (Severe)
Nasal Symptoms					
1	Runny nose				
2	Blocked nose				
3	Sneezing				
4	Itchy nose				
Eye Symptoms					
1	Itchy eyes				
2	Watery eyes				

Medication score:

“On how many days did you require use of rescue medications in the last week (tick each single medication)?”

Rescue medication	Number of days used			
	0 days	1-2 days	3-4 days	5 or more days
Antihistamine tablets				
Nasal spray				
Eyedrops				

Symptom and Medication Score (SMS) = (Symptom score/6 + Medication score/6)/2

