Appendix 8: Medication washout periods prior to visit-1, 0, 5, and 7.

Medication Washout Periods	
Medications	Time
Inhaled β-agonists	
Short acting (e.g., Salbutamol, Ventolin, Salamol Easi-Breathe, Terbutaline, Bricanyl)	6 hours
Long acting (e.g., Salmeterol, Serevent, Formoterol, Foradil, Oxis)	2 days
Oral β-agonists	
Conventional release (e.g., Salbutamol, Ventolin)	12 hours
Modified release (e.g., Bricanyl)	2 days
Cromolyn drugs (e.g., Intal, Tilade)	7 days
Leukotriene modifiers (e.g., Montelukast, Singulair, Zafirlukast, Accolate)	3 days
Inhaled corticosteroids (e.g., Beclomethasone, AeroBec, Asmabec Clickhaler, Beclanzone Easi-Breathe, Becodisks, Qvar, Budesonide, Pulmicort, Symbicort, Flixotide, Seretide, Asmanex)	14 days
Oral steroid (e.g., prednisone)	14 days
Theophylline product	14 days
Short-acting preparation (e.g., Nuelin SA, Slo-Phyllin, Aminophylline)	24 hours
Long-acting preparation (e.g., Uniphyllin Continus, Phyllocintin Continus)	2 days
Rhinitis Medications	Time
Sodium Cromoglicate (e.g., Rynacrom, Vividrin)	7 days
Antihistamines (e.g., Cetirizine, Desloratadine, Neoclaritin, Fexofenadine, Telfast, Levocetirizine, Xyzal, Loratadine, Chlorphenamine, Piriton, Atarax, Zaditen)	5 days
Decongestants (e.g. pseudoephedrine, phenylephrine)	3 days
Antihistamine-decongestant tablets/liquids (e.g., Zyrtec D, Claritin-D)	3. days
Nasal corticosteroids (e.g., Flixonase NS, Flixonase Nasules, Nasonex, Nasacort, Flonase, Nasonex, Beclomethasone, Beconase, Betnesol, Vista-Methasone, Budesonide, Rhinocort Aqua)	14 days
Médications (Prior to antigen nasal biopsy)	Time
Aspirin, NSAIDs, or other anti-platelet agents	2 days

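### Both washout lists omit Visit 6, the blinded-phase nasal challenge held soon after the pollen season; the 6-month comparison may be distorted, probably only slightly

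*Protocol*

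**What the plan says.** Protocol 6.4.8.1 points the reader to the "required medication washout periods prior to screening, nasal challenges and biopsies (V-1, V0b, V5, and V7"). The title of Appendix 8 gives the same coverage: "Medication washout periods prior to visit-1, 0, 5, and 7". Appendix 8 sets 5 days for antihistamines and 14 days for nasal corticosteroids. The sentence in 6.4.8.1 cites Appendix 7, which is the visual analogue scale used after nasal challenge, not the washout table.

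Visit 6 appears in neither list. Its description in Protocol 6.5.14 says: "Also a nasal allergen challenge with 5.000 BU/ml Timothy grass pollen allergen will be undertaken". On timing it says: "After 6 months of treatment and shortly after the pollen season patients will mark a retrospective GE VAS". The visit schedule gives Visit "6, from July to October, 2014", and SAP 7.1.1 repeats that window. Neither the Visit 6 text nor the SAP adds a washout instruction.

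Antihistamine tablets, nasal corticosteroid and antihistamine eye drops are supplied through the season (6.4.8.1). SAP 7.2.1 names the between-arm difference at 6 months among its comparisons of interest, and exploratory endpoint 5 in SAP 7.3.1 uses the 6-month response.

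**The concern.** Visit 6 gives the only measurement of the early nasal response between baseline and 12 months, in a trial whose primary objective is the time course. The baseline and 12-month challenges are done after washout. If the lists are followed as written, the 6-month challenge need not be, and it is the one closest to the period of rescue-drug use.

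Antihistamines and nasal corticosteroids suppress the symptoms that the TNSS scores; that is why Appendix 8 exists. Clinical hypothesis 3 expects "Reduction in seasonal symptoms and medication use" on active treatment. If that is right, more placebo than active participants would be challenged under residual rescue drug, the placebo response would be lowered more, and the 6-month difference would be understated.

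**Working it through.** **Coverage.** Nasal challenges of randomised participants up to month 12, from Protocol 6.5.14, against the two lists:

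| Visit | Nasal challenge | On the washout lists |
|---|---|---|
| V-1 | yes | yes |
| V0b | yes | yes |
| V5 | no (biopsy only) | yes |
| V6 | yes | **no** |
| V7 | yes | yes |

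Four challenges, three covered, one not. Visits 8 and 9 and the non-atopic Visit 1 are also unlisted, but they lie outside the blinded randomised comparison.

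**Who is exposed.** Treatment starts in January to April 2014. Six months from 1 January is 1 July; six months from 15 February is 15 August. If last rescue use is no later than 31 July (assumed), the 14-day window closes on 14 August. Exposure is then confined mainly to those who started between January and mid-February, provided Visit 6 is held at about 6 months.

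**The plan's figures.** Protocol 6.8.1 gives mean 4.63 and SD 1.65 for the AUC, and 22 per group for 80% power to detect a 30% reduction. The difference is 0.30 × 4.63 = 1.389, so the active mean is 3.241. The standard error is 1.65 × √(2/22) = 0.497. Power = Φ(1.389/0.497 − 1.96) = Φ(0.83) = 79.7%, which agrees with the stated 80%. This figure is not in dispute; it fixes the scale.

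**Share of visits inside a window (E).** Assume visits are spread evenly from the day after last use to 31 October.

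- Last use 15 July: 108 days remain; 5/108 = 4.6%, 14/108 = 13.0%.
- Last use 31 July: 92 days remain; 5/92 = 5.4%, 14/92 = 15.2%.

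**Effect on the absolute difference.** Let u_p and u_a be the rescue-use rates on placebo and active, and k the proportional cut in a user's AUC. All three are assumptions, since the documents give none of them. The arm means become 4.63(1 − E·u_p·k) and 3.241(1 − E·u_a·k), so the relative loss is

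E × k × (4.63·u_p − 3.241·u_a)/1.389.

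| u_p / u_a | Bracket ÷ 1.389 | E = 4.6%, k = 10% | E = 15.2%, k = 50% |
|---|---|---|---|
| 50% / 25% | 1.083 | 0.5% smaller | 8.2% smaller |
| 50% / 50% | 0.500 | 0.2% smaller | 3.8% smaller |
| 25% / 50% | −0.333 | 0.15% larger | 2.5% larger |

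The largest loss is 0.082 × 1.389 = 0.11 AUC units. That is 0.11/1.65 = 0.07 SD, and 0.11/0.497 is under a quarter of one standard error.

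**Dependence on scale.** Protocol 6.8.1 states its target as a percentage reduction. With equal use the factors cancel: 3.241(1 − x)/[4.63(1 − x)] = 0.70, so there is no bias on that scale. In the worst row above the ratio becomes 0.70 × (1 − 0.019)/(1 − 0.038) = 0.714, so a 30% reduction would appear as about 28.6%. If instead each user loses the same number of AUC points, equal use gives no bias on the absolute difference either, and any excess use on active reverses the sign.

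**The case against.** The strongest reply is that 6.4.8.1 speaks of nasal challenges in general, so the intent already covers Visit 6 and the bracketed list is merely incomplete. As an account of intent this is plausible, and nothing in the documents suggests a deliberate choice to challenge at Visit 6 without washout. It does not remove the problem: staff work from the listed visits, both lists omit Visit 6, and the cross-reference leads to the wrong appendix.

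A second reply stands in full. Exclusion criteria 3 and 5 (Protocol 6.3.3) remove people with symptomatic perennial allergy or with symptoms outside the grass season, and inclusion criterion 2 places peak symptoms between mid-May and mid-July. Such participants have little reason to take rescue drugs once the season is over.

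Three stronger readings are tempting and are not supported.

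- A reader might infer that recent rescue use could not be seen in the data. Appendix 5 alone would suggest so: it asks "On how many days did you require use of rescue medications in the last week", in day-bands, with the instruction "Please complete weekly on Wednesday during the pollen season from beginning of May until the end of July". But SAP 9.1 classifies CRF medications by start and stop dates, and the schedule in SAP 10.2.1 lists concomitant medications at each visit. How as-needed use is logged is not stated, so missing dates cannot be concluded.
- A reader might infer bias toward no effect even with equal use in the two arms. That holds only for proportional suppression measured on the absolute difference.
- A reader might infer a serious loss of power at 6 months. That would need something like 20% to 40% of placebo participants inside a washout window; the assumptions above imply about 2% to 8% (0.046 to 0.152, times 0.5).

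**Conclusion.** The omission is real, appears in both lists, and should be corrected. Its consequence is limited to the 6-month early-response comparison in SAP 7.2.1 and exploratory endpoint 5. The bias is toward no effect if rescue use is higher on placebo, as hypothesis 3 implies. With equal use there is none on the percentage scale, and only modest shrinkage of the absolute difference if suppression is proportional.

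The size is unknown and probably small: at most about 8% of a 30% difference, or 0.11 AUC units, given evenly spread visits, 50% against 25% use, and a 50% cut in a user's AUC. This is not a strict ceiling. The loss is proportional to E, so it rises if visits bunch just after the season, and it is zero if all visits are on or after 15 August with last use by 31 July.

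It would be wrong to infer that the 12-month primary endpoint is compromised: Visit 7 is on both lists and is not directly affected. Severity is minor.

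**What to change.** Add Visit 6 to the visit lists in Protocol 6.4.8.1 and Appendix 8, and change the reference in 6.4.8.1 from Appendix 7 to Appendix 8. Schedule Visit 6 within its existing July to October window once the participant's washout is complete. Confirm the last rescue use in the concomitant-medication review already scheduled at that visit; the CRF start and stop dates described in SAP 9.1 may already capture it, so check this before adding any item. Keep all Visit 6 challenges in the main 6-month analysis: dropping those inside a window would condition on use after randomisation and could itself bias the contrast.

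The cost is a text correction to two lists and one reference. Some visits will move later: a participant first dosed on 1 January and seen on 15 August is at 226 days, about 7.4 months. Participants also go without rescue drugs for up to 14 days, which should be tolerable after the season given the exclusion criteria. The lists already ask for the same at Visit 5, during the season.

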6.4.8.2. Prohibited Medications

Use of the following medications is prohibited during study participation:

- β -blockers.
- Calcium channel blockers.
- Tricyclic Antidepressants.
- Monoamine oxidase inhibitors.
- Anti-IgE monoclonal antibody treatment.

6.5 Study Procedures

6.5.1 General assessments

- Informed consent
- Medical history
- Allergy history
- Comprehensive physical examination (includes height and weight)
- Vital signs: blood pressure, temperature, pulse, and respiratory rate
- Adverse events

6.5.2 Clinical procedures

- Nasal challenge
- Nasal fluid collection
- Nasal brushing
- Nasal biopsy
- Peak nasal inspiratory flow (PNIF)
- Pulmonary function testing (spirometry)
- Peak flow testing (PeakFlow)
- Intradermal skin test: Timothy grass – *Phleum pratense*
- Skin prick test: grass pollen (timothy grass), silver birch (*Betula verrucosa*), mugwort (*Artemisia vulgaris*), house dust mite (*Dermatophagoides pteronyssinus*), cat hair (*Felis domesticus*), dog hair (*Canis familiaris*), horse hair (*Equus caballus*), common moulds: *Aspergillus fumigatus*, *Cladosporium herbarum*, *Alternaria alternata*, plus negative (diluent) and positive (Histamine dihydrochloride) controls.

6.5.3 Local laboratory assessments

- Urine pregnancy test
- Haematology: Complete blood count with differential
- Total IgE

- Timothy grass specific IgE

6.5.4 Questionnaires

- Global evaluation scores (GE) (**Appendix 1, 2, 4**)
- miniRhinoconjunctivitis Quality of Life Questionnaire (mRQLQ) (**Appendix 3**)
- Symptom medication score (SMS) (**Appendix 5**)
- Total nasal symptom score (TNSS) (**Appendix 6**)
- **Medication Diary cards for Tablet count (Appendix 9)**

6.5.5 Pollen count

Pollen counts will be quantitated retrospectively for the purposes of analysis. *Pollen season* is defined as follows:

Start of season	First 3 consecutive days at pollen count >10 grains/cm ³
End of season	First 3 consecutive days at pollen count < 10 grains/cm ³
Start of peak season	First 3 consecutive days at pollen count >30 grains/cm ³
End of peak season	First 3 consecutive days at pollen count < 30 grains/cm ³

6.5.6 Nasal wash (lavage)

Boiled water allowed to cool to lukewarm is added to a purpose made squeezable plastic 240 ml bottle (Sinus Rinse, NeilMed, USA). A single sachet of pharmaceutical grade sodium chloride and sodium bicarbonate is then added to the water and mixed to form a solution. After testing again to ensure a suitable temperature, the nozzle of the bottle is placed into the volunteer's nose to form a seal, and, with the volunteer leaning forward over a sink, the bottle is then squeezed to allow a jet of solution to pass into one nostril and out of the other. The process is then carried out into the other nostril and repeated several times until all of the solution has been used. SinuRinse® is widely available and no adverse effects are to be expected.

6.5.7 Nasal allergen challenge

Nasal allergen challenge is performed with Aquagen SQ (ALK 225) Timothy grass pollen, *Phleum pratense*, ALK-Abelló freeze dried extract (Cat. no. 1001862, ALK-Abello, Denmark). Fresh extracts will be reconstituted in albumin-based diluent (ALK-Abello) on a weekly basis at a concentration of 100,000 SQ-U / 30,000 BU per ml. On a daily basis, a fresh dilution of 5,000 BU/ml in normal saline will be prepared from the stock solution. This solution will be added to a nasal applicator device (Bidose, Aptar Pharma/Pfeiffer, Germany), designed to spray a standard volume (100µL) with each metered dose pump application. A single spray will be applied to each nostril, giving a total allergen dose of 1,000 BU. Following the nasal challenge the EPR will be measured using the TNSS (**Appendix 6**). A score $\geq 7/12$ points after 5 minutes during screening will be interpreted as a positive response and patients will be included in the study. If during screening the proportion of patients not being included in the study because of this inclusion criterion exceeds 20% the cut-off for inclusion will be lowered to ≥ 5 points.

6.5.8 Sampling of nasal secretions

Open cell flexible polyurethane foam (Zuschnitt Schaumstoff RG27 grau, Gummi-Welz GmbH & Co, Germany, ISO 5999, 1982 sponge) pre-cut into rectangular blocks 20 x 15 x 5 mm will be used to collect secretions. Sponges will be autoclaved for 20 minutes at 121°C in batches of 20. A fresh batch will be used for each volunteer. The patient will be sitting comfortably upright with the head facing forwards. A sponge will be placed into each nasal cavity, posterior to the muco-cutaneous junction, under direct visualization using blunt-ended forceps and a nasal speculum. Sponges will be left in place for up to 5 minutes before removal using the same instruments. Following removal, each sponge will then be placed above a microfilter within a centrifuge tube and kept on ice. Tubes will then be centrifuged for 10 minutes at 4,500 rcf at 4°C. The volume of freed fluid will be calculated by weight using an electronic balance. The fluid will then be aliquoted into eppendorf tubes and frozen at -80°C.

6.5.9 Intradermal skin tests

Intradermal skin tests are performed by injecting 0.02ml of allergen diluted in albumin-based diluent into the skin of the outer surface of the forearms. 1 BU (0.02ml of 50

BU/ml) will be injected into the right and the left forearm. A negative control injection of 0.02ml of normal saline will be injected on the outer surface of the wrist on the right.

Skin responses are defined as follows:

Response	Skin Allergen Challenge
Early Phase Response (EPR)	Measured 15 Minutes after Allergen Challenge \pm 5 min
Late Phase Response (LPR)	Measured 8 Hours after Allergen Challenge \pm 1 hour

In pollen sensitized individuals, allergen skin injection provokes a local wheal and flare skin response, peaking at about 15 minutes. This is recorded in comparison with the negative control (saline) injection. In sensitized, allergic individuals, following resolution of the early wheal and flare response, there is a gradual onset mild swelling and redness over a larger area around the site of the injection – the LPR. This response is measured at 8 hours after injection using a pencil-friction technique to map out the extent of skin swelling. Volunteers may experience mild to moderate itchiness or local discomfort at the sites of intradermal injections and skin pricks with allergen. The symptoms are not bothersome and treatment with oral antihistamines is always available and is effective although almost never required. Systemic reactions including anaphylaxis after skin tests with standardized aeroallergen extracts are a theoretical risk but exceedingly rare. However, a physician is always present and drugs and equipment for treatment of anaphylactic reactions available.

